## Methods

### Study design

In this study we will include adolescent participants with Osgood-Schlatter, presenting as anterior knee pain localized to the tibial tubercle (OSD-group), and a matched group of pain free controls (control group), matched on sex, age (<1 year group difference) and type of sports (weightbearing vs non-weightbearing). The study will be conducted at the International Olympic Research Center - Copenhagen (Sports Orthopaedic Research Centre - Copenhagen), at Hvidovre University Hospital. The project will be initiated March 2023, with recruitment of 26 participants: 13 participants in the OSD-group, and 13 in control group.

Approval has been obtained from the ethical review board of the Capital Region of Denmark (H-20072873), and the Data Management Agency of Capitol Region of Denmark (P-2021-73).

### Recruitment

Recruitment will happen through social media advertisement, from patients referred to the Osgood-Schlatter clinic at the orthopedic department, Hvidovre University Hospital, and from local sport clubs. Participants from the control group, will be rewarded with a movie ticket after participation.

All possible participants will be screened over the phone, before clinical examination and are included if criteria is met.

#### Patients and guardians' consent

Before engaging in trial, participants and their parents/guardians will receive a pamphlet with written information. During their visit, they will receive verbal information and instructions regarding the context and aim of the study. Written consent will be collected from the parents/guardians of the participants, and verbal consent from the participants.

#### Processing of personal data

All personal data will be stored on logged secured servers, provided by the Capitol Region of Denmark. Journals of the treated cases will be stored electronically as per standard care.

### Participants

#### Inclusion criteria

- Patients must be 9-16 years of age
- Presence of pain for 12 weeks or more
- Pain at tibial tubercle during loading activities
- Palpable pain at the tibial tubercle

#### Exclusion criteria

- Previous knee or hip surgery
- Other main diagnose of anterior knee pain (patellofemoral pain, Sinding-Larsen Johansson disease, Jumpers knee, etc.)
- Hip and/or back pain interfering with activities of daily living or physical activities
- Suspicion of other main diagnose such as meniscal tears and or ligamentous tears
- Unable to communicate verbally or orally in Danish

#### Clinical examination and treatment

The study procedures will be conducted by two examiners (JL and HS). JL will be aware of the case status and conducts the screening and preliminary testing. To avoid bias, examiner HS will be blinded for the case status during trial and will not know the Numerical pain Rating Scale-scores (NRS, 0-10, 'no pain' to 'worst pain imaginable') of the participants during testing. To strengthen the inter-reliability, the examiners will not change roles during the study.

The session starts with JL examining the potential participant in the OSD-case group, for Osgood-Schlatter. If the Osgood-Schlatter diagnosis is made, the participant is then enrolled. For the potential participant in the control group, JL screens for potential injury or pain in relation to the knee joint. In the absence of relevant pathology, the control-participant is enrolled.

Then, JL measures length of the lever arm and variables for peak hight velocity assessment. Participants will then answer the patient-reported outcome measures together with their parent/guardian.

For the rate of force development tests, HS will enter the room and conduct the tests as described below. For each attempt the participant will write down their NRS-rating on a piece of paper, out of sight from HS.

Before the rate of force development test is conducted, the participants are told that they can always abort the test, if they perceive that pain rises to such a degree that they can't continue the

testing, or they start feeling fearful or uncertain of their symptoms. They are ultimately told that potential pain felt during testing are not harmful and will subside within 24 hours, as is our experience from multiple earlier conducted tests.

HS leaves the room, for JL to conduct the Anterior Knee Pain Provocation test and save the NRS results.

HS returns to conduct the Counter Movement Jump Test, again blinded for the participants NRS-scores, which are written down on a piece of paper. HS leaves the room, and JL either treats the patient (case-group) or hands out compensation for participating (control-group).

Cases and controls will be instructed not to take any pain medication 24 hours prior to any assessment to ensure that this does not affect measurements.

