## Methods

The study design and analysis strategy have been published along with a trial registration (ClinicalTrials.gov NCT05789095). The study will include 13 adolescent participants with Osgood-Schlatter and a group of 13 pain free controls matched on sex, age, and sports participation on the group level. Testing will include bilateral rate of torque development measurements of knee extension and flexion, with a fixated handheld dynamometer, during a single test-session lasting approximately two hours. The examiner responsible for strength-testing will be blinded to case-status. Along with anthropometric data, participants will perform the anterior knee pain provocation test to assess pain-response to sustained knee loading, a countermovement jump test to assess power and jump height, and provide patient-reported measures of condition severity, pain, disability, and quality of life. Data collection will start February 2023 and is expected to be completed by May 2023.

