### Knee extension

The participant is sitting with  $90^\circ$  hip flexion, knee flexed approximately  $60^\circ$ , with test leg resting in testers hand, and feet free of the floor. They will be instructed to hold onto the back of the examination table and keep their upper body upright. A strap fixated to the bottom of the examination bed, is used to fixate the handheld dynamometer anteriorly on the shin, corresponding to the line of lever demarcation. If the participant feels the metal of the gauge on their shinbone through the padding of the dynamometer, extra padding will be placed on the shin.

The participant will be instructed to *press against the dynamometer as fast and hard as possible, and to keep pushing until instructed to relax* (approximately 3-4sec.). Standardized verbal instruction is provided before each trial by the tester: *3-2-1-go-push-push-push and relax*. For the knee flexion, the participant will be instructed to bend their knee, and for the extension, to straighten the leg.

Participants will perform two test trials: one at 50% of self-estimated maximal force, and one at 100%. The assessor will hold the leg in starting position to allow full rest between trials, lasting 1-minute. Three maximal attempts are recorded. One tester will hold the dynamometer and instruct the patient (HS), while one tester (JL) manage data collection software (Hoggan Health Industries 2000, version 11.0.1, Quest Medical Group, Inc.). The order of the movements is decided by coin

toss. The affected leg is tested first in each movement. In the control group the affected leg will be decided by coin toss before tester HS enters the room.

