## Risks and adverse events

In this context, adverse events will be any unintended symptoms or findings during examination, or severe increase in pain intensity during testing, to such extend that testing can't continue. In the case of adverse events, the data relevant to the participant will be excluded, and a new participant enrolled. A participant that can't continue due to pain intensity will be treated with caution and observed for potential pain increase. If needed, they will be set in contact with a medical doctor from the orthopedic department, at Hvidovre University Hospital and still receive treatment/compensation. 48 hours after testing, a phone consultation will be made, to make sure that the pain intensity has decreased.

If problems with equipment or testing should occur to such an extent that test protocol can't continue, a new date will, if possible, be set. Or else a new participant will be enrolled, and treatment/compensation is provided to the former participant.

In the case of unintended unblinding during testing (if allocation is revealed to HS), the data will be excluded from the collection due to risk of bias. If possible, a new set of participants (case and control) will be included, otherwise, subgroup analysis with participants with breach of blinding omitted will be performed.

An expected result from the test protocol is temporary pain and muscle soreness from the muscle force tests, in both cases and controls. Furthermore, an increase in symptoms from Osgood-Schlatter may be present after testing, in the case group. To our knowledge, this presents no safety hazard to the participants.

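### Case status is concealed from the strength examiner by several sound steps, but cues available during hands-on testing are not masked and a status that is inferred is never recorded

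*Combined protocol and SAP*

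**What the plan says.** The summary under Methods makes the claim without qualification: "The examiner responsible for strength-testing will be blinded to case-status". The section Clinical examination and treatment repeats it ("will be blinded for the case status during trial and will not know the Numerical pain Rating Scale-scores") and sets out how it is achieved.

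- One examiner, who knows the case status, does the screening, diagnosis and lever-arm measurement. The roles are never exchanged.
- The strength examiner comes in for the strength tests, leaves for the provocation test and returns for the jump test. Treatment or compensation follows after that examiner has left.
- Pain scores are written down out of the strength examiner's sight.
- Controls are given a nominal affected leg, so that test order does not betray the group: "In the control group the affected leg will be decided by coin toss before tester HS enters the room".
- The spoken instruction is standardised, and its wording is printed under Knee extension.

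During the strength tests this same examiner holds the dynamometer, supports the leg and instructs the participant. In extension a strap is used to "fixate the handheld dynamometer anteriorly on the shin, corresponding to the line of lever demarcation". Risks and adverse events has a rule that begins "In the case of unintended unblinding during testing". It applies if allocation is revealed to the strength examiner. The data are then excluded and a new case and control are included if possible; failing that, an analysis omits the participants concerned.

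**The concern.** The listed measures control what the strength examiner is told. They do less about what that examiner can see, hear or feel while handling the limb. The inclusion criteria define a case by pain at the tibial tubercle on loading and on palpation, and the strength tests load that structure. Participants are told that they may abort because of pain or fear, and Risks and adverse events expects symptoms to be provoked in cases. Writing the score on paper hides the number but not a wince, a hesitation, a remark or an early stop.

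This matters because of how the result will be read. Expected results and implications names the main interest as a deficit in non-symptomatic limbs or in flexion, to be interpreted as inhibition at a central level. RTD is a maximal voluntary effort. If an examiner who has inferred the status urges, braces or holds differently, the effect could appear in every limb and movement of that participant, which is the same pattern. Blinding is the study's defence against this alternative explanation, and the plan has no means of showing whether it held.

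**Working it through.** **1. Exposure.** Both legs and both movements are tested, giving 2 × 2 = 4 limb-movement tests. Knee extension specifies two practice trials and three maximal attempts. If the practice trials are repeated for each test (an assumption), 4 × (2 + 3) = 20 contractions are performed under this examiner's hands. Half of them, 10, are in flexion.

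**2. Cues set against controls.**

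| Route to case status | Control in the plan |
|---|---|
| Diagnosis, screening | Other examiner; strength examiner absent |
| Provocation test | Strength examiner absent |
| Pain score | Written, out of sight |
| Which leg is tested first | Coin toss in controls |
| Wording of the instruction | Script |
| Appearance of the knee | None stated |
| Remarks by child or parent | None stated |
| Pain behaviour or aborting | None stated |
| Status inferred but not revealed | Outside the wording of the unblinding rule; no record |

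**3. Which comparisons are exposed.** Hypotheses 1, 3, 4 and 6 compare cases with controls. Hypotheses 2 and 5 compare the two knees of the same case. A shift b common to all of a case's tests enters the first set in full. In the second set it gives (affected + b) − (other + b) = affected − other, so it drops out to the extent that b is the same for both legs.

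**4. The plan's own figure.** Inputs from Sample size: difference 6 − 3 = 3 Nm/kg/s, SD 2.6, two-sided 5%, 80% power. Standard error = 2.6 × √(2/13) = 1.02; noncentrality = 3/1.02 = 2.94; 24 degrees of freedom; critical t = 2.064. Power from the noncentral t is 80.6% with 13 per group and 77.1% with 12. The stated 13 is reproduced and is not affected by this point.

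**5. Illustration of bias.** The documents give no size for examiner influence, so the shift is assumed. With no true difference, 13 per group and SD 2.6:

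| Assumed shift (share of a mean of 6) | Noncentrality = shift/1.02 | Two-sided false positives | Of these, cases falsely lower |
|---|---|---|---|
| 0 | 0 | 5.0% | 2.5% |
| 0.3 (5%) | 0.29 | 5.9% | 4.7% |
| 0.6 (10%) | 0.59 | 8.7% | 8.2% |
| 0.9 (15%) | 0.88 | 13.5% | 13.3% |
| 1.2 (20%) | 1.18 | 20.4% | 20.3% |

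The shift is the average over the whole case group. If only half the cases were recognised and each was shifted by 10%, the average would be 0.5 × 0.6 = 0.3, which is the second row. The plan's test is two-sided, so the third column is the one to quote.

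**The case against.** A reader might infer that the blinding amounts to little more than hiding pain scores. The documents do not support that: there are separate fixed roles, planned absences, a sham affected leg and a script. A reader might also picture the examiner working on a bare knee at the lesion. Clothing is not described. The lever line runs to about two centimetres above the lateral malleolus, so the dynamometer sits near the ankle, and in flexion the participant lies prone. The strength examiner is not asked to palpate the tubercle, and the case criteria name no visible sign.

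The script limits differential coaching, although it fixes words and not tone or the firmness of the hold. The unblinding rule does not say how allocation must come to be revealed, so an obvious disclosure by speech or behaviour can reasonably fall under it. What escapes is the unspoken suspicion.

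A common remedy, asking the examiner to guess the group after testing and analysing by guess, also meets a fair objection. Someone who has just felt weak efforts will tend to guess case, so correct guesses would exceed chance under perfect concealment if the hypothesis is true. Splitting 26 participants by guess would leave very small cells.

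These arguments narrow the point. They do not supply a control for the last four rows of the first table.

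**Conclusion.** The concealment procedures are real and deserve credit. The remaining gap is specific: cues during hands-on testing are not masked, participants and parents are not asked to stay silent about symptoms, and inferred status goes unrecorded. The case-control comparisons, including the one that would be read as central inhibition, are exposed. The within-person comparisons are largely protected.

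A reader might go further and conclude that the examiner will be unblinded, or that the results will be biased by 5 to 10%. Neither follows. Whether status would be inferred, whether that would change achieved RTD, and in which direction are all unknown from the documents. The 5.9 to 8.7% range rests wholly on an assumed shift against cases, averaged over the group, with the plan's SD of 2.6 and a mean of 6. The sample size stands. This is an inexpensive improvement to make before testing; it is not a flaw that invalidates the design.

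**What to change.** **In Clinical examination and treatment**, add that before the strength examiner enters, the other examiner (a) puts the same loose, opaque covering over both knees of every participant, case or control, ending above the dynamometer line, and (b) asks child and parent not to mention symptoms, diagnosis or group to the strength examiner. The covering should be in place again when that examiner returns for the jump test. The lever arm has already been measured by then, so the covering does not interfere with it.

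**In Risks and adverse events**, add that the strength examiner notes any suspected case status together with the cue that prompted it: speech, appearance, pain behaviour or weak performance. Report these notes descriptively by group. Add a sensitivity analysis omitting participants whose status was suspected from a cue other than performance. Do not stratify by guess or set an above-chance criterion. The sensitivity analysis will be less precise: for the planned difference, power is 77.1%, 73.1% and 68.5% with 12, 11 and 10 per group. Omitting participants suspected because of pain behaviour may also remove the more symptomatic cases, so the result should be read as supportive only.

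**Cost:** coverings, one line on the case form and about a minute per participant, with no extra staff, tests or participants. The blinding claim may have to be qualified in the report.

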## Hypotheses

The hypotheses being tested are

1. that adolescents with Osgood-Schlatter, has a lower knee extension RTD in their affected knee compared to matched controls
2. that adolescents with Osgood-Schlatter, has a lower knee extension RTD in their affected knee compared to their potential asymptomatic knee
3. that adolescents with Osgood-Schlatter, has a lower knee extension RTD in their potential asymptomatic knee compared to matched controls
4. that adolescents with Osgood-Schlatter, has a lower knee flexion RTD in their affected knee compared to matched control
5. that adolescents with Osgood-Schlatter, has a lower knee flexion RTD in their affected knee compared to their potential asymptomatic knee
6. that adolescents with Osgood-Schlatter, has a lower knee flexion RTD in their potential asymptomatic knee compared to matched controls
7. That levels of either early or late rate of torque development is negatively correlated with pain during rate of torque development-testing, countermovement jump height or power, anterior knee pain provocation test score, current pain, pain duration, KOOS child 'Pain', 'Sport/rec' or 'QoL' subscales,

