#### Patient Reported Outcome Measures

Participants will fill out a questionnaire, containing some basic information about their pain experience, such as: duration of pain, previously received treatment, current pain, worst pain during past 24 hours and week. Furthermore, there are questions about activity level, as well as questions from Knee Injury and Osteoarthritis Outcome Score (KOOS-child) and Tampa Scale of Kinesiophobia (TSK-17).

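### The current-pain rating used in hypothesis 7 is taken after an examination that must include painful palpation in cases, and no unprovoked rating is scheduled at any other point

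*Combined protocol and SAP*

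**What the plan says.** All references are to the combined protocol and SAP.

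- **Recruitment:** pre-screening is remote. "All possible participants will be screened over the phone, before clinical examination and are included if criteria is met".
- **Inclusion criteria:** one criterion for cases is "Palpable pain at the tibial tubercle".
- **Clinical examination and treatment:** the visit of a potential case begins with the unblinded examiner's examination for Osgood-Schlatter. "If the Osgood-Schlatter diagnosis is made, the participant is then enrolled". Lever-arm and growth measurements come next, and after them: "Participants will then answer the patient-reported outcome measures together with their parent/guardian". The blinded examiner enters only after that, for the strength tests.
- **Patient Reported Outcome Measures:** the questionnaire asks for "current pain, worst pain during past 24 hours and week".
- **Hypotheses, item 7:** the proposed correlates of RTD include "anterior knee pain provocation test score, current pain, pain duration".
- **Descriptive variables:** pain intensity is otherwise listed as descriptive.

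**The concern.** A rating of current pain taken soon after the sore spot has been pressed may mix the adolescent's pain on arrival with pain left over from the examination. In cases, pain on pressing the tubercle is a condition of entry. Controls are pain free, and their screening is not said to include palpation of the tubercle, so any carry-over would fall mainly or wholly on cases.

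At stake is the interpretation of one correlate in hypothesis 7. With few participants there is little room for avoidable error in that variable, and an unprovoked value cannot be recovered once the visit is over.

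**Working it through.** **1. Order of events for a case** (from Recruitment and Clinical examination and treatment)

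1. Phone screen, at which palpation is impossible.
2. Diagnostic examination at the visit, then enrolment.
3. Lever-arm and growth measurements.
4. Questionnaire, including current pain.
5. Strength tests, with a pain rating at each attempt.
6. Anterior knee pain provocation test, with pain rated just before and just after the hold.
7. Jump test, with pain ratings.

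The palpation criterion can be confirmed only at step 2. The plan does not describe the manoeuvre, so this is an inference, but one that is hard to avoid. Pain on loading, also a criterion, can be taken from history, and the point does not depend on it.

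**2. Is there another unprovoked rating?** No. The ratings at steps 5 and 7 belong to the tests. The rating before the hold at step 6 follows the maximal strength tests. The plan gives no washout interval and no instruction to disregard examination pain.

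**3. What is not touched.** The sample size uses a difference of 6 − 3 = 3 Nm/kg/s and an SD of 2.6, so d = 3/2.6 = 1.154. A two-sided two-sample t-test at 5% alpha and 80% power (noncentral t) needs 12.83 per group, rounded up to 13. Power at 13 per group is 80.6%. The plan's figure reproduces, and no pain rating enters it. Hypotheses 1 to 6 compare RTD only.

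**4. Possible effect if cases are analysed alone.** Assumptions, none from the documents: true current pain has SD 2 points on the 0–10 scale, and carry-over is independent of both true pain and RTD. Then

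multiplier = SD_true / √(SD_true² + SD_carry²)

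| Carry-over SD | Multiplier | A true r of −0.55 would appear as |
|---|---|---|
| 0 | 2/√4 = 1.00 | −0.55 |
| 0.5 | 2/√4.25 = 0.97 | −0.53 |
| 1 | 2/√5 = 0.89 | −0.49 |
| 2 | 2/√8 = 0.71 | −0.39 |

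The value −0.55 is only illustrative. It is roughly the smallest correlation that reaches two-sided p < 0.05 with 13 cases: 2.201/√(11 + 2.201²) = 0.55, where 2.201 is the critical t on 11 degrees of freedom. The last row is extreme, because carry-over would make up 4/8 = half of the observed variance.

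For scale, the 95% Fisher interval for r = −0.55 with n = 13 is tanh(−0.618 ± 1.96/√10), about −0.85 to 0.00. Every row of the table lies inside it.

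**5. Possible effect if cases and controls are pooled.** With equal groups, raising every case's pain by m points adds 0.25 × m × (mean RTD in cases − mean RTD in controls) to the covariance. With the plan's assumed means this is 0.25 × m × (3 − 6) = −0.75m. The variance of pain changes too, so the net effect on r is not fixed, but it can be an exaggeration. In the limiting case where every unprovoked rating is zero, no correlation exists, and the shift alone would create a negative one.

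**6. Which case applies?** Hypothesis 7 does not say whether cases are analysed alone or pooled with controls, and Statistical methods describes only group comparisons. The direction therefore cannot be settled from the documents.

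**The case against.** The strongest reply has four parts.

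- **No carry-over is documented.** Nothing in the plan says that pain from palpation persists until the questionnaire. Other measurements come in between, and one examiner performs every examination, which limits variation. This stands. A reader might infer that cases' ratings are inflated and the correlation weakened. The documents support only that this may happen.
- **The attenuation formula may not apply.** It needs carry-over unrelated to RTD. Lingering tenderness could track severity, and Rationale and background proposes that local tissue pain limits rapid activation. This also stands, and is why the table in the working is an illustration and not an estimate.
- **A rating close to the strength tests may be the more relevant one.** The plan never defines current pain as unprovoked, and confirming eligibility before handing out questionnaires is a sensible order. This has some force. But pain in the test state is already captured at every strength attempt and is a separate correlate in hypothesis 7. What the plan lacks is the unprovoked value.
- **The reach is narrow.** This stands. One correlate in the last of seven hypotheses is affected, and no hypothesis compares current pain between groups.

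A reader might also infer that worst pain in the past 24 hours is equally compromised. It changes only if the examination hurt more than anything else in that day, and it appears in no hypothesis. Its exposure is marginal.

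**Conclusion.** The point holds as a minor sequencing weakness. As scheduled, the current-pain rating in hypothesis 7 may include pain provoked by the examination in cases, and the plan provides no unprovoked rating to replace it. This rests on the stated order of the visit and on the inference that palpation takes place at the examination.

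Neither the size nor the direction of an effect can be derived. Under the assumptions of independence, cases only and a true SD of 2, the multiplier for a carry-over SD of 0 to 2 runs from 1.00 (no effect) to 0.71. In a pooled analysis the correlation could be exaggerated instead.

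It would be wrong to read this as a threat to the main result. Early RTD at 0–100 ms, hypotheses 1 to 6 and the 13 per group are unaffected.

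**What to change.** Record the current-pain item after consent and before any palpation of the knee, and state in the plan that this value is the current pain of hypothesis 7. The 24-hour and week items can move with it for convenience. The rest of the session can stay in its present order. If the order cannot be changed, word the item as pain on arrival, before the examination, although this relies on short recall.

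The cost is a few unused ratings from adolescents who then fail the examination. Blinding is unaffected, because the blinded examiner enters only for the strength tests.
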